#### **4.4.1.3 Serious Adverse Events**

##### **4.4.1.3.1 Last Vaccination**

The last vaccination before an SAE will be derived from the last visit number provided in the clinical database and will be calculated as follows:

- If an SAE has a non-missing visit number, the visit number will be used to determine the last vaccination before the SAE
- If the visit number is missing, then the start date of the SAE will be used to determine the last vaccination before the SAE

##### **4.4.1.3.2 Time to Onset**

Time to onset will be computed using the same methodology as for unsolicited non-serious AEs described in Section 4.4.1.2.3.

##### **4.4.1.3.3 Duration**

Duration will be computed using the same methodology as for unsolicited non-serious AEs described in Section 4.4.1.2.4.

#### **4.4.2 Immunogenicity**

##### **4.4.2.1 Computed Values for Analysis**

To appropriately manage extreme values (< LLOQ [lower limit of quantification] and  $\geq$  ULOQ [upper limit of quantification]) for analysis purposes, the following computational rules will be applied to the values provided in the clinical database for each blood sample drawn, as appropriate:

If a value is < LLOQ, then use the computed value LLOQ/2

If a value is between  $\geq$  LLOQ and < ULOQ, then use the value

If a value is  $\geq$  ULOQ, then use the value ULOQ

#### 4.4.2.2 Seroprotectiona

If the computed value is  $\geq 40$  (1/dil) at pre-vaccination or at post-final vaccination, then the derived seroprotection indicator will be “Yes” for that test at pre-vaccination or at post-vaccination, otherwise seroprotection will be “No” – for pre-vaccination or for post-vaccination as indicated by the data. Note: If the computed value is missing, seroprotection will be missing.

#### 4.4.2.3 Fold-risea

The derived endpoint fold-rise will be driven by both baseline and post-final vaccination computed values and will be computed as follows. Generally, for extreme values, this algorithm minimizes the numerator and maximizes the denominator.

If the baseline computed value is < LLOQ and the post-final vaccination computed value is < LLOQ then the fold-rise will be 1

If the baseline computed value is  $\geq$  LLOQ and the post-final vaccination computed value is  $\geq$  LLOQ then the fold-rise will be post-final vaccination computed value/baseline computed value

If the baseline computed value is  $\geq$  LLOQ and the post-final vaccination computed value is < LLOQ then the fold-rise will be (LLOQ/2)/baseline computed value

If the baseline computed value is < LLOQ and the post-baseline computed value is  $\geq$  LLOQ then the fold-rise will be post-final vaccination computed value/LLOQ

Any titer reported as > ULOQ will be converted to ULOQ before the fold-rise calculation

#### 4.4.2.4 Seroconversiona

If a pre-vaccination titer is < 10 (1/dil) and a post-final vaccination titer is  $\geq 40$  (1/dil), or a pre-vaccination titer is  $\geq 10$  (1/dil) and there is a  $\geq 4$ -fold increase in post-final vaccination titer, then the derived seroconversion indicator will be “Yes” for that test, otherwise seroconversion will be set to “No”.

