12.3.2 Immunogenicity

For the computations, LLOQ and upper limit of quantification (ULOQ) will be managed as follows:

- If a titer is < LLOQ, then LLOQ/2 will be used
- If a titer is \geq LLOQ and < ULOQ, then the titer itself will be used
- If a titer is \geq ULOQ, then ULOQ will be used

Missing data will not be imputed. No search for outliers will be performed.

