### 5.2.2 Full Analysis Set

The FAS is defined as those subjects who have received at least 1 dose of the study vaccine and have a valid post-final vaccination serology result for at least 1 strain.

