### 5.2.3 Per-Protocol Analysis Set

The PPAS is a subset of the FAS. The subjects presenting with at least 1 of the following relevant protocol deviations will be excluded from the PPAS:

- Subject did not meet all protocol-specified inclusion criteria or met at least 1 of the protocol specified exclusion criteria
- Subject did not complete the vaccination schedule including a partially administered vaccination/dose
- Subject did not complete the second dose of study vaccine with a definitive contraindications as defined in the protocol after the first dose
- Subject received a vaccine dose other than the one that he/she was assigned to receive, or was assigned by mistake to another age group
- Preparation and/or administration of vaccine was not done as per-protocol
- Subject did not provide a post-dose serology sample in the proper time
- Subject received a protocol-prohibited therapy/medication/vaccine that might impact antibody response to the study vaccine
- Any other deviation identified during conduct of the study and judged by the clinical team during data review as having a potential impact on the assessment of immunogenicity

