### **5.3.2 Immunogenicity**

For the computations, LLOQ and ULOQ will be managed as follows:

If a titer is < LLOQ, then LLOQ/2 will be used.

If a titer is  $\geq$  LLOQ and < ULOQ, then the titer itself will be used.

If a titer is  $\geq$  ULOQ, then ULOQ will be used.

Missing data will not be imputed. No search for outliers will be performed.

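### SAP 4.4.2.4, read literally, counts a subject with an incomplete titer pair as not seroconverted, against the plan's own no-imputation rule

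*SAP*

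**What the plan says.** - **Seroconversion (SAP 4.4.2.4).** *Yes* requires either a pre-vaccination titer below 10 with a post-final titer of at least 40, or a pre-vaccination titer of at least 10 with at least a 4-fold rise. In all other cases, "otherwise seroconversion will be set to" *No*. There is no third category.
- **Seroprotection (SAP 4.4.2.2).** The rule has the same yes/otherwise-no form but adds: "If the computed value is missing, seroprotection will be missing".
- **Missing data.** SAP 5.3.2 states "Missing data will not be imputed", and Protocol 12.3.2 says the same.
- **Fold-rise (SAP 4.4.2.3).** "The derived endpoint fold-rise will be driven by both baseline and post-final vaccination computed values". It lists four cases by whether each value is below or at/above the LLOQ, and it has no catch-all.
- **Full Analysis Set (SAP 5.2.2).** Subjects must have received a dose and "have a valid post-final vaccination serology result for at least 1 strain". A baseline titer is not required.
- **Per-Protocol Analysis Set (SAP 5.2.3).** The only serology exclusion concerns the post-dose sample. Neither a missing baseline nor a result missing for one strain is named. Only the open-ended last item, for deviations "judged by the clinical team during data review as having a potential impact on the assessment of immunogenicity", could remove such a subject.

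The seroconversion definitions in Protocol 9.3.2.1 and 12.1.3.2, SAP 5.1.3.2 and SAP Table 5.1 give no rule for incomplete pairs and no denominator. SAP 5.1.3.1 sets denominators for safety only.

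**The concern.** Assigning *No* to a pair whose outcome cannot be determined imputes non-response. The specific derivation rule therefore says one thing and the general missing-data rule another, and the SAP does not say which governs. The note under seroprotection shows that its authors saw the need for an exception to this kind of rule. They wrote it for one of the two binary endpoints only.

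Two results follow if 4.4.2.4 is programmed as written. The seroconversion rate is pulled down whenever pairs are incomplete. It also rests on n subjects, while the geometric mean titer ratio for the same strain rests on n − m, because an incomplete pair has no fold-rise value. In a study with no hypothesis tests, the estimates and their intervals are the whole output, and seroconversion is one of four listed immunogenicity parameters.

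**Working it through.** The documents state no seroconversion rate and no number of incomplete pairs, so there is no plan figure to reproduce. The check has three parts.

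**1. Can incomplete pairs enter the analysis?** Yes, in two ways under SAP 5.2.2: a subject with a post-final result but no baseline, or a subject with a post-final result for some strains only. A subject with no post-final result for any strain is outside the Full Analysis Set and is not affected.

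**2. Which incomplete pairs are truly undetermined?** All possible titers were enumerated (5 for below LLOQ, up to 10240, including geometric means of duplicates one dilution apart).

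| Missing value | Value present | Possible outcomes |
|---|---|---|
| Baseline | Post below 40 | *No* only |
| Baseline | Post 40 or above | *Yes* or *No* |
| Post-final | Baseline 2560 or below | *Yes* or *No* |
| Post-final | Baseline above 2560 | *No* only, given the 10240 cap (10240/4 = 2560) |

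The second and third rows are the ones where a *No* amounts to imputation.

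**3. How far does the rate move?** Inputs: n = 60, taken from the planned group size (SAP 5.5) and assumed to be the number in the analysis set; m incomplete pairs, assumed; x responders among the n − m complete pairs, assumed; exact Clopper-Pearson 95% intervals, as in SAP Table 5.1.

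- Missing left missing: x/(n − m)
- Literal 4.4.2.4: x/n = [x/(n − m)] × (n − m)/n

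| m | Missing left missing | Literal rule | Loss (points) |
|---|---|---|---|
| 0 | unchanged | unchanged | 0 |
| 1 | 53/59 = 89.8% (79.2–96.2) | 53/60 = 88.3% (77.4–95.2) | 1.5 |
| 3 | 40/57 = 70.2% (56.6–81.6) | 40/60 = 66.7% (53.3–78.3) | 3.5 |
| 3 | 51/57 = 89.5% (78.5–96.0) | 51/60 = 85.0% (73.4–92.9) | 4.5 |
| 6 | 27/54 = 50.0% (36.1–63.9) | 27/60 = 45.0% (32.1–58.4) | 5.0 |
| 6 | 38/54 = 70.4% (56.4–82.0) | 38/60 = 63.3% (49.9–75.4) | 7.0 |
| 6 | 49/54 = 90.7% (79.7–96.9) | 49/60 = 81.7% (69.6–90.5) | 9.1 |

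At rates near 30% the losses are 0.5, 1.5 and 3.0 points for m = 1, 3 and 6.

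**A half-way rule is also biased.** Suppose only the certain *No* results (baseline missing, post below 40) were kept and the undetermined pairs dropped. Assume a true rate of 70%, 85% of subjects with post of at least 40, and m baselines missing at random. The expected rate is 0.7 × (60 − m)/[(60 − m) + 0.15m]. For m = 6 this is 37.8/54.9 = 68.9%; for m = 3 it is 39.9/57.45 = 69.5%. The literal rule gives 63.0% and 66.5%. Both approaches fall below 70%; excluding every incomplete pair does not.

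**The case against.** The best counter-argument is that SAP 5.3 is the section on missing data and its immunogenicity rule is unqualified. The conditions in 4.4.2.4 presuppose a pair of titers, so its final clause can be read as separating responders from non-responders among evaluable pairs. On that reading the effect is zero. This is a fair reading, and the text does not prove how the analysis will be run. But 4.4.2.4 does not limit itself to complete pairs, whereas 4.4.2.2 took care to deal with a missing value. Two competent programmers could therefore produce different rates.

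Second, m is probably small. Baseline blood is a Visit 1 step before vaccination for every subject, and ordinary dropouts without post-final results are already outside the Full Analysis Set. Nothing in the documents suggests 6 of 60. At m = 0 or 1 the loss is at most 1.5 points, and even 3.5 points is small beside an interval 25 points wide. This stands as a limit on the size, not as an answer to the contradiction.

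Third, Table 5.1 calls for numbers and percentages, so a reader could work out afterwards which denominator was used. That is true, but it does not settle the rule in advance.

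Fourth, the sentence for fold-rise is not strictly needed, since an incomplete pair already has no value there. That is also correct; the addition is for consistency.

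**Conclusion.** The point holds. As written, SAP 4.4.2.4 codes undetermined pairs as non-response. It lacks the exception that seroprotection has, and it conflicts with SAP 5.3.2 and Protocol 12.3.2. The literal rule can only lower the seroconversion rate or leave it unchanged. With n = 60, complete-pair rates of about 30% to 90% and m from 0 to 6, the loss is 0 to 9.1 points. The upper end needs 10% of pairs incomplete and a rate near 90%, and m is an assumption throughout. There is no hypothesis test and no seroconversion threshold, so the consequence is an understated rate and interval, or one that depends on the programmer's reading, and not a wrong decision. It should be fixed before the derivations are programmed.

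**What to change.** Add to SAP 4.4.2.4: *If the pre-vaccination or post-final vaccination titer for a strain is missing, seroconversion for that strain is missing and the subject is excluded from that strain's denominator.*

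Put the matching sentence in 4.4.2.3, so that fold-rise and seroconversion visibly share one denominator per strain. Apply the rule to every incomplete pair, including those where *No* would be certain.

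The cost is one sentence in each of the two subsections and a guard in the derivation code. No change to data collection or to the protocol is needed.

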### 4.4.3 Efficacy

Not applicable.

### 4.4.4 Derived Other Variables

#### 4.4.4.1 Age for Demographics

To calculate age in months at enrollment for subjects 6 months to <36 months of age, the following algorithm will be used:

---

a Post-final vaccination is defined as 28 (window, 28–35) days post-final vaccination for subjects 6 months to < 9 years of age, and 21 (window, 21–28) days post-vaccination for subjects  $\geq$  18 years of age.

- The difference in years will be calculated by subtracting the year of birth from the year of the enrollment visit; this difference will be multiplied by 12 to get the difference in months
- The month of birth will be subtracted from the month of the enrollment visit
- The values calculated above will be added to obtain a provisional age in months
- It will be determined when the day of the enrollment visit (e.g., the 31st day of the month) occurred relative to the day of birth (e.g., the 28th day of the month). The final age in months will be determined as follows:
  - a) If the day of the enrollment visit  $\geq$  day of birth, then the sum calculated above will be considered the final age in months; otherwise,
  - b) If the day of the enrollment visit  $<$  day of birth, then the sum calculated above will be reduced by 1 month to obtain the final age in months

To calculate age in years at enrollment for subjects  $\geq$  3 years of age, the following algorithm will be used:

- The difference in years will be calculated by subtracting the year of birth from the year of the enrollment visit.

Age in years will also be calculated using the following formula:

$[(\text{date of the first vaccination}) - (\text{date of birth}) + 1]/365.25$ , rounding to the first decimal place.

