## **3 Description of the Overall Trial Design and Plan**

### **3.1 Trial Design**

### **3.2 Trial Plan**

This is a Phase IV, multi-center, open-label study of a planned 240 subjects to describe the safety and immunogenicity of Fluzone Quadrivalent vaccine in children 6 months to < 9 years of age, adults 18 to < 65 years of age, and to describe the safety and immunogenicity of Fluzone High-Dose vaccine in adults  $\geq$  65 years of age. Each subject will be assigned to the appropriate age group based on the subject's age at the time of enrollment. An approximately equal number of subjects from each group will be enrolled at each site.

- Group 1: Children 6 to < 36 months of age assigned to receive a 0.25-mL pediatric dose of Fluzone Quadrivalent vaccine (60 subjects planned)
- Group 2: Children 3 to < 9 years of age assigned to receive a 0.5-mL dose of Fluzone Quadrivalent vaccine (60 subjects planned)
- Group 3: Adults 18 to < 65 years of age assigned to receive a 0.5-mL dose of Fluzone Quadrivalent vaccine (60 subjects planned)
- Group 4: Adults  $\geq$  65 years of age assigned to receive a 0.5-mL dose of Fluzone High-Dose vaccine (60 subjects planned)

All subjects will receive an intramuscular dose of their assigned vaccine during Visit 1. For subjects 6 months to < 9 years of age for whom 2 doses of influenza vaccine are recommended per guidance from the Advisory Committee on Immunization Practices, a second dose of the same volume of Fluzone Quadrivalent vaccine as the first dose will be administered at Visit 2 (28 [window, 28–35] days after Visit 1).

Subjects 6 months to < 9 years of age (Group 1 and Group 2): blood specimens will be obtained from all subjects prior to the first vaccination and 28 (window, 28–35) days following the final vaccination (Visit 2 for subjects receiving 1 dose; Visit 3 for subjects receiving 2 doses) and assayed for immunogenicity. Solicited adverse reaction (AR) information will be collected for 7 days after each vaccination. Unsolicited non-serious adverse event (AE) and serious adverse event (SAE) information will be collected from Visit 1 to Visit 2 for subjects receiving 1 dose or from Visit 1 to Visit 3 for those subjects receiving 2 doses.

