## 5.1 Statistical Methods

Summaries of the recruitment and baseline demographic characteristics of the study subjects will be presented. The number of subjects enrolled and their age at enrollment (mean [with standard deviation (SD)], quartiles, minimum and maximum), sex, race, and ethnic origin will be summarized, along with the number and description of protocol deviations.

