### 5.2.4 Populations Used in Analyses

Baseline and demographic analyses will be performed on all enrolled subjects.

The safety analyses will be performed on the Safety Analysis Set.

The immunogenicity analyses will be performed on both the FAS and PPAS.

---

a for which safety data are scheduled to be collected.

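### SAP 4.4.4.1 derives age in years for subjects aged 3 and over without a birthday step, so an eligible Group 2 or Group 3 subject can be reported at or above the group's upper age limit; SAP 5.1 does not name the age it tabulates

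*SAP*

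**What the plan says.** SAP 4.4.4.1 sets out three age derivations.

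- **Age in months, 6 to < 36 months.** Differences in years (times 12) and in months are added. If the day of the visit is earlier than the day of birth, "then the sum calculated above will be reduced by 1 month to obtain the final age in months".
- **Age in years at enrollment, 3 years and over.** There is one step: "The difference in years will be calculated by subtracting the year of birth from the year of the enrollment visit". Nothing follows it.
- **A second age in years.** "Age in years will also be calculated using the following formula": first vaccination date minus birth date plus 1, divided by 365.25, "rounding to the first decimal place". It carries no age restriction and no stated use.

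SAP 5.1 summarizes "their age at enrollment (mean [with standard deviation (SD)], quartiles, minimum and maximum", and SAP 5.2.4 gives the population: "Baseline and demographic analyses will be performed on all enrolled subjects". Neither section names the derived variable.

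The age groups are in SAP 3.2. Group 2 is 3 to < 9 years, and the next is "Group 3: Adults 18 to < 65 years of age assigned to receive" the 0.5-mL Quadrivalent dose. Protocol 5.2.4 sets eligibility by age on the day of first vaccination. Its footnote closes the child range on the day before the 9th year, which I read as the 9th birthday.

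**The concern.** The months rule and the years rule do the same job for different ages, but only the months rule checks whether the anniversary has been reached. The year difference therefore gives one year too many to anyone whose birthday falls between the visit and 31 December. Enrollment is planned from September 2017, so a sizeable share of birthdays will still be to come.

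The two ages in years refer to the same day, since "All subjects will receive an intramuscular dose of their assigned vaccine during Visit 1", yet they can disagree on completed years. Two programmers following this SAP could report different maxima. If the year difference is tabulated, a correctly enrolled child can appear as 9 in the group that ends before 9, and an adult as 65 in the group that ends before 65. Either reads like an eligibility deviation that did not happen.

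**Working it through.** The plan gives no figure of its own to reproduce, so the rules were applied as written.

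**Inputs from the documents.** Rules: SAP 4.4.4.1. Group limits and 60 planned per group (180 aged 3 and over): SAP 3.2. Study period September to December 2017: protocol 5.1.5. Visit windows: up to 35 days per interval for children, up to 28 days for adults.

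**Assumptions, not in the documents.** Birthdays uniform over the year. Ages uniform within group for the counts at the limits. Enrollment uniform from 1 September to a cut-off.

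**Worked examples, visit on 20 September 2017**

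| Born | Completed years | Year difference | Date formula |
|---|---|---|---|
| 15 Nov 2008 | 8 | 2017 − 2008 = 9 | 3232/365.25 = 8.8 |
| 15 Nov 1952 | 64 | 2017 − 1952 = 65 | 23686/365.25 = 64.8 |

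**Share shown one year too old.** For a given visit date this is the days left in 2017 divided by 365: 121/365 = 33% on 1 September, 91/365 = 25% on 1 October, 60/365 = 16% on 1 November, 30/365 = 8% on 1 December.

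**Averages over enrollment windows.** The last enrollment dates that still allow completion by 31 December are 22 October (two-dose child, 2 × 35 days), 26 November (one-dose child, 35 days) and 3 December (adult, 28 days). A window ending 30 September is added for fast enrollment. The share falls linearly, so its mean is the average of the two end values: for 30 September, (121 + 92)/2/365 = 0.292.

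- Overstated, of 180 = 180 × share.
- Group 2 shown as 9 = 60 × share/6 (six single years of age; only the oldest can reach 9).
- Group 3 shown as 65 = 60 × share/47.
- Chance of at least one = 1 − (1 − p)^60, with p = share/6 or share/47.

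| Enrollment 1 Sep to | Share | Overstated, of 180 | Group 2 shown as 9 | Chance of ≥ 1 | Group 3 shown as 65 | Chance of ≥ 1 |
|---|---|---|---|---|---|---|
| 30 Sep | 0.292 | 52.5 | 2.9 | 95% | 0.37 | 31% |
| 22 Oct | 0.262 | 47.1 | 2.6 | 93% | 0.33 | 28% |
| 26 Nov | 0.214 | 38.5 | 2.1 | 89% | 0.27 | 24% |
| 3 Dec | 0.204 | 36.7 | not applicable (past the child cut-off) | – | 0.26 | 23% |

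**Direction.** The year difference is never below completed years, and enumeration of eligible birth dates found no case under a lower limit. Only a maximum can leave its group. Group 4 ages are overstated equally often, but that group has no upper limit.

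**Mean.** Completed years run 0.50 below exact age on average. The year difference adds the share back: −0.50 + 0.29 = −0.21 to −0.50 + 0.20 = −0.30. The year rule is therefore not further from the exact mean, and no bias in the mean is claimed.

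**Would the date formula do?** It removes the one-year error. Rounded to one decimal, it prints 9.0 once days + 1 reaches 3269 (3269/365.25 = 8.95). The last eligible value is 3287, so this covers 3287 − 3269 + 1 = 19 birth dates, or 60 × 19/2191 = 0.5 of 60 in Group 2. The Group 3 band is also 19 days: 60 × 19/17166 = 0.07 of 60. Truncated to whole years it never reaches either limit (3287/365.25 = 8.9993; 23741/365.25 = 64.9993), and it equals completed years for 99.8% of eligible birth dates.

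**The case against.** The strongest reply is that the error appears only if the year difference is tabulated, and nothing in the documents says it is. The date-based age is in the same section, applies to all four groups, and suits a summary by mean, SD and quartiles. This stands as a condition on the consequence. It does not repair the plan: the two definitions coexist without assigned uses, and the label in SAP 5.1 matches the heading of the uncorrected rule, which is suggestive but not decisive.

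Three further points have merit. Whether an age is wrong depends on the benchmark, and against exact age a birthday step moves the mean further down; the gain is in individual values and the maximum. A Group 3 breach is unlikely, so Group 2 is the practical case. And printing 9.0 a few days before a birthday is ordinary rounding; truncation matters only where the value is set against a group limit, and no such comparison is planned.

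No endpoint, interval or analysis set changes, so this is a correction to a descriptive table.

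**Conclusion.** The concern holds and is minor. As written, the years rule gives ages one year too high for subjects whose birthday is still to come, and the SAP does not say whether that age or the date-based one is reported. If the year difference is reported, about 20–29% of subjects aged 3 and over are affected, an impossible-looking Group 2 maximum of 9 is likely (about 2–3 children of 60), and a Group 3 maximum of 65 is possible but unlikely (0.3–0.4 expected of 60). These frequencies rest on the uniform birthday, age and enrollment assumptions and on a calendar the protocol calls approximate; the existence of the error does not. Allocation runs through the interactive response system at enrollment (protocol 6.5), so grouping, eligibility, per-protocol membership, safety and immunogenicity are untouched.

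**What to change.** Make one of two changes in SAP 4.4.4.1:

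- (a) Add a birthday step to the years rule: subtract 1 year if the month and day of the enrollment visit come before the month and day of birth. This gives completed years, which cannot reach 9 or 65 for an eligible subject.
- (b) Delete the year-difference rule and keep the date-based age, truncating rather than rounding wherever it is set against group limits. Because demographics cover all enrolled subjects, use the enrollment date for anyone enrolled but not vaccinated.

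In either case, name the chosen variable in SAP 5.1 as the age that is summarized. The cost is one or two SAP sentences and a line of code. Date of birth is already collected at Visit 1 (protocol 5.1.4).
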